4.4 Unscheduled Visits

Due to the complexity of the study, no unscheduled visits will be permitted.

4.5 Subject Completion/Withdrawal

For subjects with CP who were naïve to pancreatic enzyme medication at the start of the study, at the end of participation in the study (all collections are complete for Visit 2) Creon36™ will be discontinued and they will resume their usual care without pancreatic enzyme medication. For subjects with CP who were receiving pancreatic enzyme medication prior to the start of the study,

at the end of participation in the study (all collections are complete for Visit 2), Creon36™ will be discontinued and they will resume their usual care and will resume the pancreatic enzyme product and dose they were receiving before the study began.

Subjects may withdraw from the study at any time without prejudice to their care. They may also be discontinued from the study at the discretion of the Investigator for lack of adherence to study treatment or visit schedules, or adverse events. The Investigator or the Sponsor may also withdraw subjects who violate the study plan, or to protect the subject for reasons of safety or for administrative reasons. It will be documented whether or not each subject completes the clinical study. If the Investigator becomes aware of any serious, related adverse events after the subject completes or withdraws from the study, they will be recorded in the source documents and on the CRF.

5 STUDY EVALUATIONS AND MEASUREMENTS

5.1 Screening and Monitoring Evaluations and Measurements

5.1.1 Medical Record Review

Variables that will be abstracted from the medical chart (paper or electronic):

- Date of birth - Age 30-75 years old
- Sex
- CP diagnosis: Participants with CP will be characterized based on the TIGAR-O (toxic, genetic, autoimmune, recurrent, obstructive) etiology system, on pancreatic morphology (Cambridge criteria) when available, and on physiological state (exocrine and endocrine function) as recommended by the recent American Pancreatic Association Practice Guidelines⁴.
- History of unintentional weight loss or history of increased stools per week
- Other clinical signs or symptoms suggestive of fat malabsorption
- History of pancreatic enzyme use
- History of allergy to pork, Current diagnosis of gout and treatment with allopurinol medical therapy, or intestinal blockage or fibrosing colonopathy
- All medications, particularly medications that alter fat absorption (weight loss medications or ursodeoxycholic acid)

5.1.2 Laboratory Evaluations

Serum 25-dihydroxyvitamin D and pre-albumin (vitamin A) will be assessed at CHOP laboratories. Serum retinol and α -tocopherol [vitamin E] will be assayed at Craft Laboratories. PIVKA II ([name], Tuft's University, Medford, MA) and/or undercarboxylated osteocalcin % (UCOC %) will be assessed for vitamin K status ([name], Yale University, New Haven, CT). Zinc and selenium will be assessed at CHOP Laboratories using standard techniques. This will provide additional evidence for vitamin, mineral and essential fatty acid status resulting from pancreatic disease that may be improved with pancreatic enzyme medication in subjects with RPF/PI indicated by the MBT, CFA% and BC response. For subjects with CP, safety measures include results from serum comprehensive metabolic panel (CMP) and complete blood count with differential (CBC) performed at CHOP Laboratories using standard techniques. The CMP will provide serum albumin, total protein, bilirubin and liver enzymes to provide additional liver and nutritional status information for

the CP cohort. Also linoleic acid (essential fatty acid panel) will be assessed at ARUP Laboratories for the CP cohort only. All individuals from institutions outside of CHOP will receive only coded, not readily identifiable, samples for analyses and are not otherwise engaged in human subjects' research.

5.1.2.1 Pregnancy Testing

A urine pregnancy test will be performed for pre-menopausal female subjects.

5.1.3 Other Evaluations and Measures

Genetic Testing: Saliva will be collected for DNA sequencing of all exons and intronic junctions of all major pancreatitis risk factor genes, including PSSR1, CTSC, CFTR and SPINK1,⁴⁴⁻⁴⁷ in the CP group only. Results for additional genes that have been reported as CP disease associated will also be sequenced (CaSR, CEL, CPA1, PRSS2-3, SBDS, UBR1, and two SNPs near CLDN2). (Ariel Precision Medicine, Pittsburgh, PA). Saliva samples are stable long term (>2y) and can be stored at room temperature to ship in batches.

Fecal Elastase-1: Pancreatic function will be assessed for the CP group by fecal elastase-1 to determine the level of pancreatic enzyme activity in the stool^{51, 52} (Joli Diagnostics, Williamsville, NY). Subjects will be provided with the stool collection kit and proper instructions and supplies, and samples will be collected during the day of the visit if possible, or at home and returned. The stool sample will be stored at -20°C, and analyzed with a monoclonal enzyme-linked immunosorbent assay (ARUP Laboratory, Salt Lake City, UT).

Anthropometric Assessment: Weight, height, and BMI will be assessed. Measures of body composition will also be conducted for relative muscle and fat. All anthropometric techniques will follow those described by Lohman et al⁵³. Weight (0.1 kg) will be measured on a digital electronic scale (Seca, Munich, Germany) and stature (0.1 cm) on a stadiometer (Holtain, Crymych, UK). Skinfold thickness will be measured (0.1 mm) at the triceps, biceps, subscapular, and supra-iliac sites with a skinfold caliper (Holtain, Crymych, UK) to assess subcutaneous fat stores. Mid upper arm circumference measured with a non-stretchable fiberglass tape (0.1 cm) (McCoy, Maryland Heights, MO). Upper arm muscle and fat area Z scores will be generated^{54, 55}.

Body Composition: Total body composition, total FFM and FM and percent body fat (%FAT), will be assessed by the skinfolds using prediction equations adapted for children, adolescents, and adults^{56, 57}. Body composition will also be assessed by dual energy x-ray absorptiometry

(DXA) whole body scans (Delphi A, Hologic, Inc., Bedford, MA) for subjects with CP only at Visit 1. DXA uses very low-dose x-ray exposures (3 mrem) and measurements are rapid, making this a suitable technique for use in children. Standard positioning and clothing techniques are used. Quality control scans are performed daily using a simulated L1-L4 lumbar spine made of hydroxyapatite encased in epoxy resin, and a whole body composition phantom. A difference of >1.5% from the standard will be deemed out-of-range requiring servicing by the manufacturer. Whole body will be assessed by DXA at both Visit 1 and Visit 2. The scans will be analyzed to generate traditional DXA measures: whole body Area, BMC and areal-BMD (gm/cm²). In our institution, the in vitro CV is less than 0.6% and the in vivo coefficient of variation in adults is less than 1%. A urine pregnancy test will be performed on female subjects who are pre-menopausal prior to the scan. Pregnant subjects will not be scanned and will leave the study.

Dietary Intake: Three-day weighed food records will be obtained and calories, macro- and micro-nutrient content calculated. Subjects will be provided with scales, spoons and all supplies necessary for the collection of the dietary data and will be conducted with assistance from the CTRC staff and Bionutrition Unit^{58, 59}. Dietary intake will be analyzed using Nutrition Data System for Research software version 2012 developed by the National Coordinating Center (NCC, University of Minnesota, Minneapolis, MN)⁶⁰.

Disease Classification: Participants with CP will be characterized based on the TIGAR-O (toxic, genetic, autoimmune, recurrent, obstructive) etiology system, on pancreatic morphology (Cambridge criteria) when available, and on physiological state (exocrine and endocrine function) as recommended by the recent American Pancreatic Association Practice Guidelines⁴.

Home Environment and Health Questionnaire: The questionnaire will be administered via interview by the research staff, and will consist of two sections. The Health History section has general questions about the subject's health history including documentation of medical history, recent hospital admissions and illnesses, medication, history of pancreatic enzyme supplementation, and nutrient supplement use. A Home Environment section describes aspects of environment, such as education and income level, whether on Medicaid/Medicare and household size to describe the demographic characteristics. In addition to subjects' contact information (name, address, phone numbers); contact information from two additional contacts will be collected to maintain contact with the subject in the event that the subject cannot be contacted at their primary residence.

Quality of Life Questionnaires: In order to assess the health-related quality of life (QOL), validated questionnaires will be administered to all subjects at Visit 1. For all subjects, the Medical Outcomes Study 36-Item Short-Form Health Survey (MOS SF-36), a standardized, validated healthy survey will be administered. The MOS SF-36 covers physical functioning, bodily pain, general health perception, vitality, social functioning, emotional and mental health domains^{32, 61-65}.

Patient Reported Outcomes (PROMIS): We will assess patient reported outcomes at every study visit using the following NIH developed PROMIS short forms: pain, fatigue, depressive symptoms, physical function – mobility, physical function – upper extremity, and peer relationships.

Adherence: Adherence to pancreatic enzyme medication for subjects with CP will be assessed at study Visit 2 and by phone calls. This time will also be used to trouble-shoot any barriers to adherence, and also to collect information on adverse events experienced during the course of the study.

Adverse Events Diary: Subjects will be asked about all adverse events at both Visit 1 and Visit 2, and asked to rate by intensity (mild, moderate, severe). Serious adverse events will be reported as per various policies in a timely manner to CHOP IRB, and CTRC.

5.2 Efficacy

5.2.2. Diagnostic tests, Scales, Measures

Malabsorption Blood Test (MBT): The **MBT primary outcomes** consist of parameters from pharmacokinetic analyses. The MBT consists of a simultaneous oral dose of pentadecanoic acid (PA), a free fatty acid, and triheptadecanoic acid (THA), a triglyceride with three heptadecanoic (HA) saturated fatty acids requiring hydrolysis by pancreatic lipase before HA can be intestinally absorbed (Patent # US 7402405 B2, July 22, 2008). The MBT with the PA and THA is delivered in a breakfast test meal after a 12-hour fast and 24 hours without dairy foods. Serum concentration

levels of PA and HA are assessed by gas-liquid chromatography (GC), from serum samples drawn prior to MBT and then hourly for eight hours. The MBT test meal is prepared immediately before consumption, with 5.0g of PA and 5.5g of THA blended into a test meal composed of 64g vanilla Scandishake (Axcan Scandipharm, Birmingham, AL), 6oz silk light chocolate soy milk, and 10ml microlipids (www.nestle-nutrition.com). The 8oz MBT test meal contains ~550 calories, 32 g fat, and 52% of calories from fat. The test meal was designed to be similar to a high fat dinner meal. Prior to administration of the MBT test meal, an indwelling catheter is placed for baseline (0 Hour) and subsequent blood draws at Hour 1, 2, 3, 4, 5, 6, 7 and 8 post ingestion for quantification of serum PA and HA. The MBT test meal is consumed within five minutes of the baseline blood draw. After the Hour 6 blood draw, subjects consume a 1000 kcal, low fat (12 g) lunch meal, and two blood samples will follow this meal (Hours 7 and 8). During the eight-hour protocol period, subjects are offered non-caloric and non-caffeinated beverages *ad libitum*. The 72-hour home stool collection will begin two days after the MBT visit, and the corresponding 3-day weighed food record will begin the day prior to the first day of the 72-hour stool collection.

Table 3. Protocol for each MBT visit

Protocol	Day 1	Day 2	Day 3	Day 4	Day 5	Day 6	Day 7	Day 8	Day 9
Enzyme-naïve: MBT #1 CP Healthy Comparisons	- Fast from 8pm - No dairy - No alcohol - Normal activity	- MBT at 8am - Lunch at 2pm - 9 hourly blood draws	Home Return to usual diet	- Diet record (day 1)	- Diet record (day 2) - 72-hour stool (day 1)	- Diet record (day 3) - 72-hour stool (day 2)	- 72-hour stool (day 3)		
Enzyme-naïve with washout: MBT #1 CP	Wash-out No Enzymes	Wash-out No Enzymes	Wash-out No Enzymes - Fast from 8pm - No dairy - No alcohol - Normal activity	- MBT at 8am - Lunch at 2pm - 9 hourly blood draws	Home Return to usual diet	- Diet record (day 1)	- Diet record (day 2) - 72-hour stool (day 1)	- Diet record (day 3) - 72-hour stool (day 2)	- 72-hour stool (day 3)
Pancreatic Enzyme Medication: MBT#2 CP	Enzyme treatment	Enzyme treatment	Enzyme treatment - Fast from 8pm - No dairy - No alcohol - Normal activity	- MBT at 8am - Lunch at 2pm - 9 hourly blood draws	Home Return to usual diet	- Diet record (day 1)	- Diet record (day 2) - 72-hour stool (day 1)	- Diet record (day 3) - 72-hour stool (day 2)	- 72-hour stool (day 3)

Each subject in CP cohort will have two MBT, the first on a pancreatic enzyme medication-naïve protocol and the second after three days of pancreatic enzyme medication treatment. If subjects are receiving pancreatic enzyme medication at study enrollment, after consultation with their medical team, they will be asked to discontinue pancreatic enzyme medication for three days prior to the first MBT, the day of the MBT and the five days following the MBT until the end of the 72-hour stool collection. Thus, the total number of days of data collection for the enzyme-naïve MBT protocol will be seven for subjects not receiving pancreatic enzyme medication at Visit 1, and nine for those requiring a washout period from pancreatic enzyme medication (see **Table 3**). For the MBT that will be administered with pancreatic enzyme medication, subjects will take pancreatic enzyme medication for three days prior to the MBT. Each day, the pancreatic enzyme medication dose will be 72,000 lipase units per meal and 36,000 units per snack using Creon 36,000 units per capsule. They will take two Creon36™ (72,000 lipase units) with the MBT on the morning of the test meal. Pancreatic enzyme medication dose range for adults with RPF/PI is not well standardized.

The dose chosen for these short term studies are in the higher range recommended for initial treatment^{5,6}. Subjects will then continue to take pancreatic enzyme medication at home for the next five days until the 72-hour stool collection is completed. The total number of days for the pancreatic enzyme medication MBT protocol is nine (see **Table 3**). For the healthy individuals, the MBT protocol will last one week since they will be pancreatic enzyme medication -naïve.

Plasma samples will be analyzed by a GC method at Wake Forest University (Winston-Salem, NC). Total lipids are extracted from 200 μ L of plasma following the method of Bligh and Dyer⁶⁶. Following methylation of the fatty acids in the total lipid extract, fatty acid methyl esters are extracted into iso-octane and 1 μ L was injected into the GC column for analysis using a Hewlett Packard 5890 series II gas chromatograph with a programmable cool on-column capillary inlet, flame ionization detector (FID), and HP7673 auto sampler/injector. Chromatographic data collection and analysis is via a serial connection to a computer running ChromPerfect Spirit™ chromatography data system (Justice Laboratory Software, Denville, NJ). The column used is a CP-Sil 88 for FAME, 100m (L) x 0.25mm (ID) x 0.25 μ m (film thickness) (Agilent Technologies, Inc., Santa Clara, CA) with a 1m (L) x 0.53mm (ID) deactivated precolumn. Calibration curves are based on injections of methyl tridecanoate, methyl PA, and methyl HA injections. Inter-assay variability (%CV) for the measurement of PA in samples with low, medium and high concentrations (1.30, 2.99, and 6.70 mg/dL) was 2.9%, 2.6%, and 3.1%, respectively. Inter-assay variability for the measurement of HA (0.56, 1.29, 3.05 mg/dL) in the same samples is 2.6%, 4.0%, and 3.9%, respectively.

The primary outcomes for the MBT include PA and HA pharmacokinetic analyses including comparison of absorption curves, C_{max} and AUC, and percent absorption of plasma PA and HA concentrations and also the HA/PA ratio 1) between CP and the healthy reference group, and 2) with pancreatic enzyme medication exposure compared with pancreatic enzyme medication -naïve status in the CP cohort.

Utilizing the relative absorption of HA to PA, the MBT has been shown to respond to changes in fat absorption in healthy adult subjects using a lipase inhibitor and in subjects with CF and PI while on and off pancreatic enzyme therapy⁴⁹, and is also sensitive to enzyme dose titration⁵⁰.

Coefficient of Fat Absorption (CFA): The **CFA primary outcome**, the coefficient of fat absorption (CFA%) will be determined by the 72-hour stool collections at Visits 1 and 2 and a 3-day weighed food record collection while consuming a moderate fat (about 80+ g/day) diet. These stool collections will be performed at home and returned to CHOP. Subjects will be given a home collection kit and detailed instructions. Specimens will be stored frozen until analysis of total fat content by a gravimetric method (Mayo Medical Laboratories, Rochester, MN). Total dietary intake of fat during the 3-day period will be assessed from the 3-day weighed food records which will coincide with the 72-hour stool collection, and the CFA% will be calculated⁶⁷. The CFA% will be compared 1) between the CP cohort and the healthy reference group, and 2) with pancreatic enzyme medication exposure compared with pancreatic enzyme medication-naïve status in the CP cohort.

Bomb calorimetry (BC): The BC primary outcome for BC is the assessment of energy loss in the stool from the 72-hr stool collection (NIDDK sponsored research unit, Phoenix Indian Medical Center, Phoenix, AZ) using bomb calorimetry⁶⁸⁻⁷⁰. Samples will be shipped frozen and the heat of combustion (energy) will be measured in a bomb calorimeter, with energy liberated quantified in kcal/g stool. The energy loss from the stool will be compared 1) between the CP cohort and the

healthy comparison group, and 2) with pancreatic enzyme medication exposure compared with pancreatic enzyme medication -naive status in the CP cohort.

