Study Rationale	
Reduced exocrine pancreatic function or pancreatic insufficiency (RPF/PI) contributes to poor clinical outcome in a number of diseases and conditions. The incidence, mechanism and substantial adverse clinical outcomes of PI are well known in patients with cystic fibrosis (CF), and the life sustaining role of pancreatic enzyme medication in CF care is well established¹⁻³. Much less is known about the incidence and impact of RPF/PI in patients with chronic pancreatitis (CP). Reliable non-invasive screening or diagnostic tests with acceptable patient burden are not available for RPF/PI. We propose a study to evaluate the malabsorption blood test (MBT), stool coefficient of fat absorption (CFA) and stool bomb calorimetry (BC) methods as potential screening or diagnostic tests for RPF/PI. In subjects with CP, we also propose to administer pancreatic enzyme medication (Creon36™) to determine the test responses before and after pancreatic enzyme medication administration in these patients. Many patients with CP are at risk for RPF/PI yet they rarely undergo diagnostic testing. Pancreatic enzyme medication will likely improve clinical outcomes and quality of life in some of those with RPF/PI. A cohort of healthy volunteers will be evaluated with the three methods to provide essential comparison data to optimize the understanding and interpretation of the findings from the three methods and the RPF/PI cohort with CP.

Study Objective(s)	
Primary
 
Utilizing the MBT, CFA and BC methods to identify RPF/PI in subjects with CP, our primary hypotheses are:
 
H1: Subjects diagnosed with CP and not receiving pancreatic enzyme medication will have RPF/PI as indicated by the reduced MBT, CFA and BC fat and energy absorption pattern compared to healthy participants.
 
H2: Subjects with CP with reduced RPF/PI by the MBT, CFA and BC fat and energy absorption pattern will have improved fat absorption after pancreatic enzyme medication (Creon36™) as indicated by the MBT, CFA and BC increased fat and energy absorption pattern.
 
Secondary
 
The secondary objective of this proposal is to utilize these data to optimize the MBT design and application by reducing the time and blood samples required.
 
H3: The MBT will be optimized to identify RPF/PI with 3-4 blood samples (vs 9 current samples) over 4-5-hours (vs current 8-hours).

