2 STUDY OBJECTIVES

2.1 Primary Aims

2.1.1. Our first primary aim is to compare fat and energy absorption from the diet in subjects with CP and healthy subjects utilizing the MBT, CFA and BC methods to characterize fat and energy absorption patterns.

2.1.2. Our second primary aim is to determine if, in subjects with CP, fat and energy absorption will improve after pancreatic enzyme medication utilizing the MBT, CFA and BC methods to characterize the fat and energy absorption patterns.

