6.3.1 Efficacy Analysis

Statistical Analysis: H1 and H2: Descriptive statistics for MBT, CFA% and BC outcomes (mean, standard deviation, median, range, 95% CI) will be calculated for the CP cohort and for the healthy comparison group, and differences between CP and healthy groups assessed with unpaired t tests. For the MBT outcomes, a moment-based pharmacokinetic (PK) analysis will be performed based on non-compartmental methodology using WinNonLin version 9.1 (Pharsight, Cary, NC). Baseline (C_0) and maximum (C_{max}) plasma concentrations are calculated, and area under the curve from time zero to eight hours (AUC) is calculated using the linear trapezoid method. PK parameters can then be compared between treatment groups using a paired t-test or Wilcoxon signed rank test as appropriate. To describe HA exposure relative to that of PA, the ratio of the HA to PA C_{max} (C_{max} HA/PA) and AUC (AUC HA/PA) is calculated for each subject after molar transformation and dose-normalization of exposure metrics⁴⁹. Alternately, population PK analyses for repeated-measures endpoints can be conducted via nonlinear mixed-effects modeling with a qualified installation of the nonlinear mixed-effects modeling (NONMEM) software, Version VII, Level 2.0 (ICON

Development Solutions, Hanover, MD)⁴⁸. Using this method, population PK modeling is conducted by simultaneously fitting structural PK models to both PA and HA concentrations⁵⁰.

Descriptive statistics for MBT, CFA% and BC outcomes (mean, standard deviation, median, range, 95% CI) will also be calculated for the CP cohort with and without pancreatic enzyme medication administration, and the significance of changes over time assessed with paired t tests. HA and PA concentrations will be transformed to molar quantities and the ratios for HA to PA C_{max} and AUC and the associated 95% confidence interval will be calculated. A mixed effects modeling approach will be employed to examine the correlation of subject characteristics (age, BMI, sex, disease status, etc.) to PA and HA exposure metrics derived from the non-compartmental analysis to assess change over time in MBT response to pancreatic enzyme medication administration in subjects with CP. Metrics to be tested will be CFA%, PA and HA C_{max} , AUC, HA/PA C_{max} and AUC ratio and the %HA response compared to the healthy reference group. A value of $p < 0.05$ will be considered statistically significant.

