For the CFA% outcome, our experience has been in CF and PI, with average CFA% of $81 \pm 14\%$ in one study⁶⁷ and $83 \pm 10\%$ in another⁷¹ when subjects were on pancreatic enzyme medication. In comparison, in healthy subjects, CFA% is typically $\geq 93\%$. From the literature for CP, a number of clinical trials have used CFA% to describe fat malabsorption in subjects with CP and confirmed pancreatic insufficiency before and after administration of pancreatic enzyme medication. Ramesh et al¹⁵ found an increase in CFA% from 66.7 ± 14.0 before pancreatic enzyme medication to $88.9 \pm 5.2\%$ after pancreatic enzyme medication (change of $22.7 \pm 12.2\%$) in adults with CP from India. Also in adults from India participating in a placebo-controlled trial, Thorat et al¹⁶ saw CFA% increase from 66.5 ± 14.1 to $86.1 \pm 7.5\%$ in those taking pancreatic enzyme medication compared to an increase from 67.0 ± 14.0 to $72.9 \pm 11.5\%$ for placebo, a treatment effect of 13.7% (95% CI: 9.1, 18.2) after one week of pancreatic enzyme medication. From this combined experience with variability of the CFA% in both CF and CP, 21 subjects in each group will have 80% power to detect a difference in means of 10% (the difference in CFA% between health group mean of 95% and CP group mean of 85%) assuming that the common SD is 11% using a t-test with $\alpha = 0.05$.

For the BC method, there is limited information for typical variability in calories lost in stool in either healthy subjects or those with malabsorption diagnoses. Using 72-hour stool assessments, Wierdsma et al⁷⁰ has recently reported average daily energy loss of 213 ± 66 kcal in 23 healthy adults. This loss was less in those >50 years old (197 ± 49 kcal). If we assume that approximately 200 kcal/day are lost in the stool of healthy subjects, 21 subjects in each group will have 80% power to detect a difference in means of 50 kcal (the difference in BC between health group mean of 200 and CP group mean of 250 kcal lost in stool) assuming that the common SD is 56 using a t-test with $\alpha = 0.05$.

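### Bomb calorimetry is the only energy measure, yet it is analysed as stool energy loss with no intake term, so it does not by itself answer the energy-absorption part of the aims

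*Combined protocol and SAP*

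**What the plan says.** Section 2.1 sets the first primary aim as to "compare fat and energy absorption from the diet in subjects with CP and healthy subjects". The second aim and section 6.1 use the same pairing of fat and energy. In the synopsis, H2 expects improvement after enzyme "as indicated by the MBT, CFA and BC increased fat and energy absorption pattern".

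Section 5.2.2 defines the BC outcome as energy lost in the 72-hour stool collection, and that loss is what is compared: "The energy loss from the stool will be compared 1) between the CP cohort" and the healthy group, and with versus without enzyme. Section 6.3.1 (Efficacy Analysis) applies unpaired and paired t-tests. Section 6.4 powers the group comparison on "the difference in BC between health group mean of 200 and CP group mean of 250 kcal lost in stool", and the paired comparison on a fall from 250 to 214 kcal/day.

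For fat, section 5.2.2 does bring in intake: "Total dietary intake of fat during the 3-day period will be assessed from the 3-day weighed food records", and CFA% is calculated from it. On energy, section 5.1.3 says: "Three-day weighed food records will be obtained and calories, macro- and micro-nutrient content calculated". Table 1 schedules that record for both cohorts and for both CP visits.

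The documents disagree on the rank of BC. Section 5.2.2 calls it a primary outcome and Table 1 lists it under secondary outcomes. Section 6.4 restates the primary hypotheses in terms of fat absorption only.

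**The concern.** The energy found in stool depends on how much was eaten as well as on the fraction absorbed. CFA allows for this on the fat side, and the MBT uses a fixed test meal. Neither measures energy. BC does, but has no intake term.

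If CP and healthy subjects eat different amounts during the collection, or CP subjects eat differently at the two visits, stool energy can change while the absorbed fraction does not. Equally, a true change in absorption can be masked. Either way, the comparison would describe stool loss correctly and energy absorption wrongly, and no planned BC analysis would separate the two.

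**Working it through.** **Fat and energy side by side**

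| | Fat (CFA) | Energy (BC) |
|---|---|---|
| Stool quantity | stool fat | stool energy |
| Intake in the same food record | fat, used | calories, not used |
| Diet target in collection | about 80+ g/day | none stated |
| Outcome compared | percent absorbed | amount lost |

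The covariate model in section 6.3.1 relates "subject characteristics (age, BMI, sex, disease status, etc.) to PA and HA exposure metrics". The list of metrics to be tested adds CFA% but not BC.

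**The plan's own figures** (noncentral t, two-sided alpha 0.05)

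- Group comparison: difference 50, SD 56, standardised effect 50/56 = 0.893. Required n is 20.7, so 21 per group, as stated. Power is 80.6% at n=21 and 82.5% at n=22.
- Paired comparison: difference 36, SD of differences 56, standardised effect 36/56 = 0.643. Required n is 20.99, so 21. Power is 82.0% at the stated n=22.

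**Illustration of an intake shift.** The documents give no intake data, so the 10% shift is an assumption. So is the link between intake and stool energy: half proportional means that a 10% intake change moves stool energy by 5%, and full means 10%. SD stays at 56, and n is 22 per group or 22 pairs.

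Absorbed fraction unchanged; chance that the stool-loss test is significant:

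| | Half | Full |
|---|---|---|
| H1, CP intake 10% higher | 200 × 0.05 = 10 kcal/day: 8.9% | 200 × 0.10 = 20: 21.2% |
| H2, Visit 2 intake 10% lower | 250 × 0.05 = 12.5: 17.0% | 250 × 0.10 = 25: 51.5% |

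Planned effect present, shift in the masking direction; chance of detecting it:

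| | No shift | Half | Full |
|---|---|---|---|
| H1, CP intake 10% lower | 82.5% | 250 × 0.95 − 200 = 37.5: 58.3% | 250 × 0.90 − 200 = 25: 30.4% |
| H2, Visit 2 intake 10% higher | 82.0% | 250 − 214 × 1.05 = 25.3: 52.5% | 250 − 214 × 1.10 = 14.6: 21.5% |

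The shift that would reproduce the whole planned effect is 50/200 = 25% (H1) or 36/250 = 14.4% (H2) at full proportionality, and twice that (50% and 28.8%) at half.

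**What a percent-absorbed measure could deliver.** The documents give neither mean intake nor an SD for this measure. At n=22, 80% power needs a standardised effect of 0.865 (unpaired) or 0.626 (paired). Intake is assumed equal throughout.

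| Assumed intake, kcal/day | H1 effect, points (50/intake) | Largest SD for 80% power | H2 effect, points (36/intake) | Largest SD of differences | 56/intake, points |
|---|---|---|---|---|---|
| 1800 | 2.78 | 3.21 | 2.00 | 3.19 | 3.11 |
| 2000 | 2.50 | 2.89 | 1.80 | 2.87 | 2.80 |
| 2500 | 2.00 | 2.31 | 1.44 | 2.30 | 2.24 |

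The last column is the SD if every subject had the same, perfectly recorded intake. It lies just under the limits, so there is little room for food-record error.

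Differential reporting also matters. If only healthy subjects under-report, by 5% or 10%, the planned gap shrinks to (250 − 200/0.95)/50 = 79% or (250 − 200/0.90)/50 = 56% of its size.

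**The case against.** The strongest reply is that BC is not mislabelled where it is defined. Sections 5.2.2, 6.3.1 and 6.4 all speak of energy or calories lost in stool, and energy absorption is a joint label for three methods. Table 1 makes BC secondary, section 6.4 frames the hypotheses for fat only, and the study is open-label and exploratory. All of this stands and lowers the weight of the point. It does not remove it, because sections 2.1 and 6.1 still promise a conclusion on energy absorption.

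The design also makes a large intake shift less likely. Section 4.1 requires food intake that the subject considers typical for two weeks before Visit 1, healthy subjects need a stable diet and weight, and H2 is within subject over a few weeks. These conditions do not equalise energy intake. Section 6.3 plans descriptives for continuous variables, so an intake difference might well be seen. However, intake is not named there or tied to BC.

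A reader might infer that the BC t-tests or sample sizes are wrong. They are not: the tests keep their 5% error for stool loss, and the figures reproduce. A reader might also take the Visit 2 day list in section 4.3, which has no moderate-fat-diet line on Days 6–9, as evidence of a shift. The documents do not support that, since section 5.2.2 describes "72-hour stool collections at Visits 1 and 2 and a 3-day weighed food record collection while consuming a moderate fat" diet, which covers both visits. The missing line is a separate inconsistency.

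**Conclusion.** The point holds as a limit on interpretation. The comparison of stool energy loss is sound for what it measures. It supports a statement about energy absorption only if intake is similar between groups and between visits, and the plan neither sets energy intake nor uses the record that would show it.

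The sizes above are conditional on an assumed 10% systematic shift, an assumed half-to-full link between intake and stool energy, and SD 56 unchanged. The documents do not show that a shift will occur, or in which direction, so no bias has been demonstrated. It would also go too far to say that percent energy absorbed should replace kcal/day: its SD is unknown and it may be no more precise. This is an inexpensive improvement worth considering, not a correction that the trial depends on.

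**What to change.** 1. Keep stool energy loss in kcal/day as the powered BC outcome and write its formula into section 5.2.2: kcal/g × total 72-hour stool weight / 3. That section now gives only kcal/g, while section 6.4 uses kcal/day.
2. Add to section 6.3.1 a supportive measure, percent energy absorbed = 100 × (energy intake − stool energy) / energy intake, with both terms per day and intake from the 3-day weighed food record. Report it for CP versus healthy and for before versus after enzyme, as estimates with 95% CIs outside the p<0.05 criterion.
3. Report energy intake by group and visit beside it.
4. State one rank for BC in section 5.2.2, Table 1 and section 6.4.

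The cost is one derived variable from data already collected, with no new visits or samples. The drawbacks are that food-record error enters the measure, as it already does for CFA, and that its power cannot be stated from the documents.

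Separately, the Visit 2 day list in section 4.3 should be reconciled with the Visit 1 lists and the statement in section 4.2 that the visits are otherwise identical, and with section 5.2.2.
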